## **12 Health Outcome Analyses**

Not Applicable.

## **13 Interim Analysis**

No interim analysis is planned for this study.

## **14 Determination of Sample Size**

The sample size of approximately 50 randomized participants in each of the 5 treatment groups is not based on statistical power consideration due to the lack of information of AGN-241751 for the variability of change from baseline to 1 day after first dose in MADRS total score.

## **15 Statistical Software**

Statistical analyses will be performed using version 9.4 (or newer) of SAS.

## 16 Data Handling Convention

### 16.1 Visit Time windows

Table 16-1 Efficacy and Safety Analysis Visit Definitions

Derived Visit	Scheduled Visit Daya	Window
Baseline	Day 1 d (visit 2)	Last record on or before Index1 a
4-hour Post Dose	4-hour Post Dose (visit 2a)	4-hour post dose
Day 2	Day 2 (visit 3)	Index1 a +1
Day 5	Day 5 (visit 4)	Days [Index1 a +2, IndexA b -1]
Day 8	Day 8 d (visit 5)	IndexA b
Day 9	Day 9 (visit 6)	Day IndexA b +1
Day 12	Day 12 (visit 7)	Days [IndexA b +2, IndexB c -1]
Day 15	Day 15 d (visit 8)	IndexB c
Week 3	Day 22 (visit 9)	Days [IndexB c +1, day of final double-blind visit or ET Visit occurring after IndexB c +1]
End of double-blind treatment period (end of Week 3)	The last available post-baseline assessment during the double-blind treatment period	
End of safety follow-up period	The last available post-baseline assessment during the safety follow-up period.	

a Index1: Day of first double-blind dose

b IndexA: Day of second double-blind dose, if not received, use Index1 + 7 days

c IndexB: Day of third double-blind dose, if not received, use IndexA + 7 days.

d Study treatment administration in clinic.

### 16.2 Repeated or Unscheduled Assessments of Safety Parameters

Baseline is defined as the last assessment made before the first dose of double-blind study treatment. If end-of-study assessments are repeated or if unscheduled visits occur, the last nonmissing postbaseline assessment will be used as the end-of-study assessment for generating summary statistics. However, all postbaseline assessments will be used for PCS value determinations, and all assessments will be presented in the data listings.

### 16.3 Missing Date of the Last Dose of Study treatment

Since participants will receive their double-blind study treatment doses under the direct supervision of study center personnel, the date of the last dose of study treatment will be available, i.e. missing data imputation rule is not applicable.

## 16.4 Missing Severity Assessment for Adverse Events

If severity is missing for an AE that started before the date of the first dose of double-blind study treatment, an intensity of mild will be assigned. If severity is missing for an AE that started on or after the date of the first dose of double-blind study treatment, an intensity of severe will be assigned. The imputed values for severity assessment will be used for the incidence summary; the values will be shown as missing in the data listings.

## 16.5 Missing Causal Relationship to Study treatment for Adverse Events

If the causal relationship to the double-blind study treatment is missing for an AE that started on or after the date of the first dose of double-blind study treatment, a causality of yes will be assigned. The imputed values for causal relationship to double-blind treatment will be used for the incidence summary; the values will be shown as missing in the data listings.

## 16.6 Missing Date Information for Adverse Events

The following imputation rules only apply to cases in which the start date for AEs is incomplete (ie, partly missing).

### Missing month and day

- If the year of the incomplete start date is the same as the year of the first dose of double-blind study treatment, the month and day of the first dose of double-blind study treatment will be assigned to the missing fields
- If the year of the incomplete start date is before the year of the first dose of double-blind study treatment, *December 31* will be assigned to the missing fields
- If the year of the incomplete start date is after the year of the first dose of double-blind study treatment, *January 1* will be assigned to the missing fields

### Missing month only

- If only the month is missing, the day will be treated as missing and both the month and the day will be replaced according to the above procedure

### Missing day only

- If the month and year of the incomplete start date are the same as the month and year of the first dose of double-blind study treatment, the day of the first dose of double-blind study treatment will be assigned to the missing day
- If either the year of the incomplete start date is before the year of the date of the first dose of double-blind study treatment or if both years are the same but the month of the incomplete start date is before the month of the date of the first dose of double-blind study treatment, the last day of the month will be assigned to the missing day

- If either the year of the incomplete start date is after the year of the date of the first dose of double-blind study treatment or if both years are the same but the month of the incomplete start date is after the month of the date of the first dose of double-blind study treatment, the first day of the month will be assigned to the missing day

If the stop date is complete and the imputed start date as above is after the stop date, the start date will be imputed by the stop date.

If the start date is completely missing and the stop date is complete, the following algorithm will be used to impute the start date:

- If the stop date is after the date of the first dose of double-blind study treatment, the date of the first dose of double-blind study treatment will be assigned to the missing start date
- If the stop date is before the date of the first dose of double-blind study treatment, the stop date will be assigned to the missing start date

## 16.7 Missing Date Information for Prior or Concomitant Medications

For prior or concomitant medications, including rescue medications, incomplete (ie, partly missing) start dates and/or stop dates will be imputed. When the start date and the stop date are both incomplete for a participant, the start date will be imputed first.

### 16.7.1 Incomplete Start Date

The following rules will be applied to impute the missing numeric fields for an incomplete prior or concomitant medication start date. If the stop date is complete (or imputed) and the imputed start date is after the stop date, the start date will be imputed using the stop date.

#### Missing month and day

- If the year of the incomplete start date is the same as the year of the first dose of double-blind study treatment, the month and day of the first dose of double-blind study treatment will be assigned to the missing fields
- If the year of the incomplete start date is before the year of the first dose of double-blind study treatment, *December 31* will be assigned to the missing fields
- If the year of the incomplete start date is after the year of the first dose of double-blind study treatment, *January 1* will be assigned to the missing fields

#### Missing month only

- If only the month is missing, the day will be treated as missing and both the month and the day will be replaced according to the above procedure

**Missing day only**

- If the month and year of the incomplete start date are the same as the month and year of the first dose of double-blind study treatment, the day of the first dose of double-blind study treatment will be assigned to the missing day
- If either the year of the incomplete start date is before the year of the date of the first dose of double-blind study treatment or if both years are the same but the month of the incomplete start date is before the month of the date of the first dose of double-blind study treatment, the last day of the month will be assigned to the missing day.
- If either the year of the incomplete start date is after the year of the date of the first dose of double-blind study treatment or if both years are the same but the month of the incomplete start date is after the month of the date of the first dose of double-blind study treatment, the first day of the month will be assigned to the missing day

**16.7.2 Incomplete Stop Date**

The following rules will be applied to impute the missing numeric fields for an incomplete prior or concomitant medication stop date. If the date of the last dose of study treatment is missing, impute it as described in Section 15.3. If the imputed stop date is before the start date (imputed or nonimputed start date), the imputed stop date will be equal to the start date.

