## 8 Demographic and Other Baseline Characteristics

Demographic parameters (age; age group (<20, 20-29, 30-39, 40-49, 50-59, and  $\geq 60$ ); race; ethnicity; sex), baseline characteristics (weight; height; and body mass index, calculated as  $\text{weight [kg]/(height [m])}^2$ ) will be summarized descriptively by treatment group for the Safety and

mITT populations. Continuous variables will be summarized by number of participants and mean, SD, median, minimum, and maximum values. Categorical variables will be summarized by number and percentage of participants.

Medical and surgical history, psychiatric history, non-drug psychiatric treatment history, and other psychiatric history will also be summarized by double-blind treatment group for the Safety Population.

Prior medication is defined as any medication taken before the first dose of double-blind study treatment. Concomitant medication is defined as any medication taken on or after the date of the first dose of the double-blind study treatment. Any medications started after the last visit of double-blind treatment period will not be summarized but will be included in listings.

Both prior and concomitant medication use will be summarized by the number and proportion of participants in each treatment group receiving each medication within each therapeutic class for the double-blind treatment period for the Safety Population. If a participant took a specific medication multiple times or took multiple medications within a specific therapeutic class, that participant would be counted only once for the coded drug name or therapeutic class. Any prior and concomitant medications will be included in listings.

The World Health Organization (WHO) Drug Dictionary Enhanced, March 2017 or newer, will be used to classify prior and concomitant medications by therapeutic class and drug name.

The number and percentage of participants with important protocol deviations will be summarized by treatment group for randomized participants. Deviations related to the following categories will be included:

- Inclusion or exclusion criteria
- Withdrawal criteria
- Treatment or dose
- Concomitant medications

These and any additional important protocol deviations will be reviewed and documented before database lock and unblinding of treatment codes.

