**Missing day only**

- If the month and year of the incomplete stop date are the same as the month and year of the last dose of study treatment, the day of the last dose of study treatment will be assigned to the missing day
- If either the year of the incomplete stop date is before the year of the date of the last dose of study treatment or if both years are the same but the month of the incomplete stop date is before the month of the date of the last dose of study treatment, the last day of the month will be assigned to the missing day

- If either the year of the incomplete stop date is after the year of the date of the last dose of study treatment or if both years are the same but the month of the incomplete stop date is after the month of the date of the last dose of study treatment, the first day of the month will be assigned to the missing day

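### When both medication dates are partial, SAP 16.7.2 can overwrite a recorded stop month and turn a prior drug into a concomitant one

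*SAP*

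**What the plan says.** SAP 16.7 sets the order: "When the start date and the stop date are both incomplete for a participant, the start date will be imputed first".

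Two consistency rules follow. SAP 16.7.1, on the start side, tests the other date: where this "is complete (or imputed) and the imputed start date is after the stop date, the start date will be imputed using the stop date". SAP 16.7.2, on the stop side, says that if the imputed stop "is before the start date (imputed or nonimputed start date), the imputed stop date will be equal to the start date".

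Two filling rules matter here. In 16.7.1, a start without month and day, in the same year as the first double-blind dose, takes the first-dose date: "the month and day of the first dose of double-blind study treatment will be assigned to the missing fields". In 16.7.2, a stop lacking only its day, in the last-dose year, is set to month end if its month "is before the month of the date of the last dose of study treatment, the last day of the month will be assigned".

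SAP 8 classifies the drug from the resulting dates: "Prior medication is defined as any medication taken before the first dose of double-blind study treatment", and "Concomitant medication is defined as any medication taken on or after the date of the first dose of the double-blind study treatment".

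**The concern.** Both consistency rules expressly cover imputed dates. For two partial dates they address the same situation and pull in opposite directions: one moves the start back, the other moves the stop forward. The stated order decides between them, and it favours the rule that moves the stop forward, even when the stop month was recorded and the start month was only a guess.

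This is a monotherapy study in which antidepressants are prohibited (Protocol 3.1 and 7.7.1), and prior medication history is taken at screening (Protocol 2). A drug that the site recorded as stopped months before dosing could appear in the concomitant table and drop out of the prior table. If imputed dates feed the concomitant-medication category of important deviations in SAP 8, it could be flagged there too.

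**Working it through.** The plan states no figure to reproduce. The check applies the rules in the order given.

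**Inputs.** The rules are those of SAP 16.7, 16.7.1, 16.7.2 and 8. The dates are assumed for illustration: first dose 15 Jun 2018; last dose 29 Jun 2018 (first dose + 14 days, since dosing is on Days 1, 8 and 15); drug start recorded as 2018; drug stop recorded as Mar 2018.

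**Stated order**
1. Start (16.7.1, month and day missing, first-dose year): 15 Jun 2018. No imputed stop exists yet, so the 16.7.1 consistency rule has nothing to act on.
2. Stop (16.7.2, day missing, month before the last-dose month): 31 Mar 2018.
3. 31 Mar is before 15 Jun, so 16.7.2 sets the stop to 15 Jun 2018. The dates are now equal, and 16.7.1 can no longer apply.
4. Class (SAP 8): taken on the first-dose date and not before it, so concomitant only.

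**If 16.7.1 prevailed instead:** start = stop = 31 Mar 2018, so prior only, which agrees with the recorded month.

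**Displacement in the example:** 30 (April) + 31 (May) + 15 (June) = 76 days. For the other stop months with the same first dose:

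| Recorded stop | Imputed stop | Days moved to 15 Jun |
|---|---|---|
| Jan 2018 | 31 Jan | 28+31+30+31+15 = 135 |
| Feb 2018 | 28 Feb | 31+30+31+15 = 107 |
| Mar 2018 | 31 Mar | 30+31+15 = 76 |
| Apr 2018 | 30 Apr | 31+15 = 46 |
| May 2018 | 31 May | 15 |

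**Which patterns are affected.** All patterns with both dates partial were enumerated for years 2017 and 2018, with a first dose on day 12 of each month of 2018 and starts no later than the first-dose month.
- Every conflict had the start month missing. None arose with a known start month.
- With the first dose in month *m*, the class changed from prior to concomitant in *m* − 1 patterns, one for each earlier stop month in that year: 0 for January, 5 for June, 8 for September, 11 for December.
- A further 11 patterns lie wholly in the previous year. A start of 2017 with a stop of Mar 2017, for example, ends with both dates on 31 Dec 2017. The recorded stop month is lost, but the drug stays prior.
- Conflicts in total: 11 + (*m* − 1), which is 16 for June.

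These count date patterns, not participants or records.

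**Complete stop date.** If the stop were recorded as, say, 20 Mar 2018, 16.7.1 would move the start back to that day and the drug would stay prior. No error arises.

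**The case against.** The strongest reply is that the SAP is not ambiguous. A reader might infer that two live rules give opposite answers, so that the tables depend on the programmer. The text does not support that: 16.7 puts the start first, and the sequence then yields one result. What stands is that the result is wrong for these records, and that the mention of an imputed stop in 16.7.1 has no effect.

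A second reply is that treating an uncertain drug as concomitant is the cautious choice. That is reasonable where the timing is unknown. Here the recorded stop month already places the end before dosing.

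A third reply is that the situation is narrow, and this stands. A reader might infer that earlier antidepressants in general would appear as prohibited concomitant drugs. They would not. A drug whose start is recorded to an earlier year is imputed to start no later than 31 December of that year, so this route cannot make it concomitant. Nothing in the documents shows how common the affected pattern is.

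Finally, a reader might infer that protocol deviations would be inflated. SAP 8 has important deviations reviewed and documented before database lock and unblinding, and does not say that the review uses imputed dates. That consequence is possible but not established. The review would not, however, correct the medication tables.

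**Conclusion.** The point holds as a minor but definite drafting error. A written rule replaces recorded information and, in a defined set of records, reverses the prior or concomitant class. Four conditions must all hold for the class to change:
- the start month is missing;
- the stop has a month but no day;
- both dates are in the first-dose year;
- the stop month is before the first-dose month.

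Within that set the misclassification is certain if the SAP is followed literally. The size of the set cannot be derived from the documents.

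The consequences are confined to the descriptive medication summaries and to any concomitant-medication deviation check that uses imputed dates. Any reading that carries the error into the efficacy results is unsupported: the mITT definition (SAP 6) and the primary model (SAP 10.1) use no medication dates, and the intercurrent events in Protocol 10.1.3 are study discontinuations.

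**What to change.** Add to SAP 16.7 that imputation may change only missing fields, never a recorded month or year. Then settle the case where both dates are partial and the imputed start falls after the imputed stop:

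- Start month missing, stop month recorded: set the start to the imputed stop (16.7.1 prevails).
- Start month recorded, stop month missing: set the stop to the imputed start (16.7.2 prevails).

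Reversing the order for every record would not do. Suppose (assumed dates) a first dose on 5 Sep 2018, a last dose on 19 Sep 2018, a start recorded as Oct 2018 and a stop recorded as 2018. The stop imputes to 19 Sep and the start to 1 Oct. Here 16.7.2 rightly moves the stop to 1 Oct. Capping the start at the stop would put it at 19 Sep, outside its recorded month. A drug begun after the Day 22 visit (26 Sep), which SAP 8 keeps out of the summaries, would then count as concomitant.

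The cost is a few sentences and a small programming change, with no effect on other analyses. The same paragraph of 16.7.2 needs an edit anyway: it refers to a Section 15.3 that does not exist, while SAP 16.3 says no imputation of the last-dose date applies.

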**Missing month and day**

- If the year of the incomplete stop date is the same as the year of the last dose of study treatment, the month and day of the last dose of study treatment will be assigned to the missing fields
- If the year of the incomplete stop date is before the year of the last dose of study treatment, *December 31* will be assigned to the missing fields
- If the year of the incomplete stop date is after the year of the last dose of study treatment, *January 1* will be assigned to the missing fields

**Missing month only**

- If only the month is missing, the day will be treated as missing and both the month and the day will be replaced according to the above procedure

**Missing day only**

- If the month and year of the incomplete stop date are the same as the month and year of the last dose of study treatment, the day of the last dose of study treatment will be assigned to the missing day
- If either the year of the incomplete stop date is before the year of the date of the last dose of study treatment or if both years are the same but the month of the incomplete stop date is before the month of the date of the last dose of study treatment, the last day of the month will be assigned to the missing day

- If either the year of the incomplete stop date is after the year of the date of the last dose of study treatment or if both years are the same but the month of the incomplete stop date is after the month of the date of the last dose of study treatment, the first day of the month will be assigned to the missing day

## **16.8 Character Values of Clinical Laboratory Parameters**

If the reported value of a clinical laboratory parameter cannot be used in a statistical summary table because, for example, a character string is reported for a parameter of the numeric type, a coded value must be appropriately determined for use in the statistical analyses. The actual values, however, as reported in the database will be presented in the data listings.

## **17 CHANGES TO ANALYSES SPECIFIED IN PROTOCOL**

None.

